**Duration of Study:**

The study will include 3 periods: screening period (up to 7 days), treatment period (up to 14 days), and a follow-up visit (approximately on Day 28 ( $\pm 3$  days) or 14 ( $\pm 3$ ) days after the last dose for those who are discharged from the hospital before Day 14).

**Outcome Measures:****Primary Outcome Measure:**

- Proportion (%) of patients with any TEAEs during the treatment period (Baseline to Day 14)

**Secondary Outcome Measures:****Safety Endpoints:**

- Proportion (%) of patients with any AEs, SAEs and drug-related AEs during the study (Baseline to Day 14 and Day 28)
- Proportion (%) of patients with clinically significant abnormality in clinical laboratory tests and ECG during the study (Baseline to Day 14 and Day 28)
- Change in parameters for coagulopathy including [REDACTED] during the study (Baseline to Day 14 and Day 28)
- Change in parameters of cardiac function including [REDACTED] during the study period (Baseline to Day 14 and Day 28)

Changes in safety outcomes in patient populations with different Baseline levels of inflammatory biomarkers to assess the correlation of biomarker profile to safety outcomes.

**Clinical Efficacy Endpoints:**

- Change from Baseline to Day 7 and Day 14 in PaO2/FiO2 ratio
- Time to improvement of oxygenation defined as oxygen saturation (pulse oximetry)  $>93\%$  and increased  $\geq 1\%$  from Baseline breathing only room air in the 48 hours preceding the measurement during the study (Baseline to Day 28)
- Number of days without oxygen use during the study (Baseline to Day 28)
- Change from Baseline to Days 7, 14 and 28 in the score of the WHO ordinal scale
- Proportion (%) of patients with clinical improvement defined as a reduction of 2 points in the WHO ordinal scale during the study (Baseline to Day 28).
- Number of days hospitalized during the study (Baseline to Day 28)
- Proportion (%) of patients free of respiratory failure during the study (Baseline to Day 28)

- All-cause mortality rate during the study (Baseline to Day 28)

Changes in clinical efficacy endpoints in patient populations with different Baseline levels of inflammatory biomarkers to assess the correlation of biomarker profile to clinical efficacy outcomes

#### Inflammatory Biomarker Measures:

- Change from Baseline to Day 7 and to Day 14 in plasma CRP level
- Time and number of the patients to reach 50% reduction from Baseline in plasma CRP level during the treatment period (Baseline to Day 14)
- Change from Baseline to Day 7 and Day 14 in inflammatory biomarker levels including ferritin, lymphocytes and neutrophil to lymphocyte ratio.
- Change from Baseline to Day 7 and Day 14 in serum [REDACTED]  
[REDACTED]
- Change from baseline to Day 7 and Day 14 in serum [REDACTED]  
[REDACTED]

#### Biomarker Assessment for Kidney Injury

- Change from Baseline to Day 7 and Day 14 [REDACTED]
- Change from Baseline to Day 7 and Day 14 [REDACTED]

#### Biomarker Assessment for CV Endothelial Cell Damage

- Change from Baseline to Day 7 and Day 14 in [REDACTED]
- Change from Baseline to Day 7 and Day 14 [REDACTED]
- Change from Baseline to Day 7 and Day 14 [REDACTED]

#### Biomarker Assessment for Target Engagement

- Change from Baseline to Day 7 and Day 14 [REDACTED]
- Change from Baseline to Day 7 and Day 14 [REDACTED]

Additional biomarkers may be assessed as appropriated. Details about sample collection and biomarker analysis will be provided in laboratory manual.

#### Measurement of Plasma Drug and metabolite Levels

Blood samples will be collected at defined timepoints. The harvested plasma will be split into two approximately equal aliquots, labeled and stored for PK analysis. Plasma parent drug and metabolite levels will be measured by validated bioanalytical method following GLP guidance.

Additional analysis may be performed as appropriated. Details about sample collection and analysis will be provided in laboratory manual. Data will not be shared with any 3rd party.

### **Statistical Analysis**

A 2-sided alpha-level of 0.05 will be used for construction of confidence intervals. No adjustment for multiple endpoints will be employed. Although the study is not powered for hypothesis testing of secondary endpoints, p-values will be generated to aid interpretation in addition to confidence intervals about the estimates.

### **Clinical Efficacy Parameters**

Change from Baseline in the PaO2/FiO2 ratio as a continuous variable will be summarized by visit and treatment using both simple descriptive statistics and model-based estimates obtained from an analysis of covariance model with terms for treatment as a class variable and the baseline score as a continuous covariate.

Time to improvement in oxygenation will be analyzed using a Cox proportional hazards model to estimate the hazard ratio and corresponding 95% confidence interval for SIR1-365 dose vs placebo.

Number of days without oxygen use in the first 28 days will be summarized descriptively and an estimate of the difference mean numbers of days will be provided along with a corresponding 95% confidence interval based on a 1-way ANOVA model with a single term for treatment.

Descriptive summaries of WHO ordinal scale, number of days hospitalized, patients with respiratory failure and all-cause mortality will be provided.

### **Safety Parameters**

Safety parameters will be summarized using descriptive statistics for patients who receive study drug (SIR1-365 or placebo).

TEAEs are defined as AEs that commence or worsen after the first dose of study medication during the study. TEAEs will be analyzed descriptively including 2-sided 95% CI for between-group (SIR1-365 – placebo) incidence rates. TEAEs analyzed will include, but not necessarily limited to, the following:

- At least 1 TEAE
- At least 1 Related TEAE
- At least 1 SAE
- At least 1 TEAE of severe intensity
- Individual TEAE Preferred terms
- Individual TEAE Preferred terms considered related to study medication

TEAEs occurring during the 14-day treatment period will include those with onset in the first 14

days, irrespective of actual days of treatment, where study day 1 is the date of the first dose of study medication. All TEAEs with onset  $\leq$  28 days will be summarized similarly.

#### Biomarker Levels

The difference between treatments in Day 7 [REDACTED] will be analyzed using an ANCOVA model with terms for treatment as a class variable and the baseline value as a continuous covariate [REDACTED] will be log-transformed (natural log) for analysis. Comparison of the SIR1-365 group vs placebo will be constructed based on least-squares means from the model. The results will be back transformed for presentation including 95% CI constructed for both within and between treatment estimates. Timepoints other than Day 7 will be analyzed similarly.

Time (days) to 50% reduction from baseline [REDACTED] during the study will be analyzed using a Cox proportional hazards model to estimate the hazard ratio and corresponding 95% confidence interval for SIR1-365 dose vs placebo.

All biomarker level data will be summarized using descriptive statistics by treatment

#### Plasma Drug and Metabolite Levels

Plasma drug and metabolite level data will be summarized using descriptive statistics by treatment.

This study will be conducted in accordance with the guidelines for Good Clinical Practice (GCP) and GLP. Study drugs will be manufactured in accordance with the guidelines for Good Manufacturing Practice (GMP).

## 2. Introduction

### 2.1. Overview of COVID-19

Beginning in December 2019, a novel coronavirus, designated SARS-CoV-2, has caused an international outbreak of illness termed Coronavirus Disease 2019 (COVID-19). The full spectrum of COVID-19 ranges from mild, self-limiting respiratory tract illness to severe progressive pneumonia, multiorgan failure, and death.

So far, there are no specific therapeutic agents for coronavirus infections, although the corticosteroid dexamethasone and antiviral remdesivir have been recommended for patients with severe COVID-19.

There is evidence of hyperinflammatory response in patients with COVID-19 coupled with an upregulation of pro-inflammatory biomarkers including cytokines such as tumor necrosis factor (TNF- $\alpha$ ), interleukin (IL)-1 $\beta$ , IL-6, etc. and other inflammatory biomarkers such as C-reactive protein (CRP) and ferritin. The elevated plasma inflammatory biomarker levels are associated with disease severity and progression. Cytokine is produced in most types of inflammation especially in the acute phase and is important in the coordination and development of the inflammatory response. However, prolonged excess production of cytokine becomes destructive. It has been hypothesized that anti-inflammatory drugs including anti-TNF- $\alpha$  and anti-IL-1 therapies should be evaluated in patients with COVID-19 upon hospital admission to prevent disease progression to the requirement for intensive care support. Indeed, several studies have indicated clinical benefits of anti-TNF- $\alpha$  and anti-IL-1 agents in COVID-19 patients.

### 2.2. Overview of RIP1 and SIR1-365

[figure not shown]
Receptor-interacting protein 1 (RIP1) is a serine/threonine protein kinase, which was initially identified as a death domain-containing protein that interacts with the death domain of death receptor Fas. RIP1 is comprised of a kinase domain at its N terminus, a death domain at its C terminus and a RHIM (RIP homotypic interaction motif) at the middle region of the protein. The death domain and RHIM domain are both protein interaction domains. RIP1 is recruited to either Fas or to TNFR1 complex via its death domain, whereas it interacts with RIP3 via the RHIM domain.

RIP1 mediates the downstream effects of multiple biological activities including: 1) RIP1 mediates TNF $\alpha$  induced NF $\kappa$ B activation pathway in a kinase-independent manner. 2) RIP1 mediates caspase8-FADD dependent apoptosis pathway in a kinase-dependent manner. 3) RIP1 mediates RIP3-MLKL dependent necroptosis pathway in a kinase-dependent manner. 4) RIP1 suppresses caspase-8 dependent apoptosis in a kinase-independent manner. 5) RIP1 suppresses ZBP1-RIP3-MLKL dependent necroptosis in a kinase-independent manner. 6) RIP1 mediates cytokine production and secretion in myeloid cells in a kinase-dependent but cell death-independent manner. 7) RIP1 mediates RIP3-kinase-dead-mutant-induced apoptosis in a kinase-independent manner.

Therefore, RIP1 inhibitors may be advantageous over selective inhibitors for a specific cytokine to reduce inflammatory response.

Genetic removal of RIP1 in a mouse model led to perinatal death, caused by the loss of RIP1's ability to suppress caspase8-dependent apoptosis and ZBP1-RIP3-MLKL dependent necroptosis. Both suppressing abilities require RIP1's function as a scaffold protein instead of its kinase activity. Nevertheless, mice containing RIP1 kinase dead knock-in mutants showed no defect in development and growth, indicating RIP1's kinase activity is not essential for embryonic development or for animal growth. Moreover, RIP1 kinase dead knock-in mice were resistant to various animal disease models, such as TNF $\alpha$ -induced systemic inflammatory response syndrome (SIRS), chronic intestine inflammation, autoimmune skin disorder, and multiple sclerosis.

RIP1 protein contains a unique allosteric pocket located in its kinase domain, which allows the development of highly selective type III kinase inhibitors. Using several different RIP1 kinase inhibitors in various animal models has demonstrated that blocking RIP1's kinase activity could prevent TNF $\alpha$  induced systemic inflammatory response syndrome, alleviate the progression of Alzheimer's disease, amyotrophic lateral sclerosis, male reproductive aging, chemotherapy-associated kidney injury, ischemia reperfusion injury to organs such as heart, brain, retina, and kidney, as well as colitis and multiple sclerosis.

[figure not shown]
Sironax, Ltd

SIR365-US-101 Clinical Study Report

Product Name: SIR1-365

Study Number: SIR365-US-101

## 2.4. Summary of Clinical Data

The following studies have been completed in Australia:

- A randomized, double-blinded, placebo-controlled SAD study and MAD study were conducted in Australia to evaluate the safety, tolerability and PK of SIR1-365 in healthy adult volunteers. The results demonstrated that a single oral administration of SIR1-365 at 10, 30, 100, 300 and 600 mg and multiple doses at 50 mg TID, 100 mg TID, 200 mg TID were safe and well tolerated by the study subjects. The reported AEs were mild to moderate events with no need of intervention and resolved in a few days. No subject discontinued from the study. PK data showed a good dose proportionality of plasma SIR1-365 concentrations at the 5 single dose and 3 multiple dose cohorts in healthy volunteers. Peak plasma exposure was achieved around 1-2 hours after dose, and the half-life ( $T_{1/2}$ ) was around 6-7 hours depending on the doses.
- A randomized, open-label, single-dose, 2-way crossover study was conducted to assess the effect of food on bioavailability of SIR1-365 tablet after a single oral dose at 100 mg. The results of this study demonstrated that food does not significantly affect the bioavailability of SIR1-365 after oral administration. Thus, SIR1-365 oral tablets can be administered before or after meal.
- An open-label study was conducted to assess the PK profile of SIR1-365 given as an oral disintegrated suspension. The results of this study demonstrated that the plasma SIR1-365 concentrations-time curves and PK parameters were comparable when SIR1-365 was administered at a single oral dose of 100 mg either as a disintegrated suspension in the suspension PK study or as a solid tablet in the SAD study. Thus, SIR1-365 tablets can be administered as a disintegrated suspension via a gastric tube in those patients who cannot swallow the tablets.

- An open-label study was conducted to assess possible inhibitory effects of SIR1-365 on the activities of CYP450 isoforms 2C19 in healthy volunteers using sensitive index substrate omeprazole. The results of this study demonstrated that SIR1-365 can inhibit the activity of CYP450 isoform 2C19. Thus, medications that are mainly metabolized via CYP450 isoform 2C19 should be excluded in patient studies.

## 2.5. Benefit/Risk Assessment

RIP1 inhibitors may be beneficial for treatment of severe COVID-19. However, no RIP1 inhibitors have been assessed in large clinical studies for any indication.

The SAD and MAD studies showed that a single oral administration of SIR1-365 at 10, 30, 100, 300, and 600 mg and repeated oral administration of SIR1-365 at 50, 100 and 200 mg, TID for 10 days were safe and well tolerated. The reported AEs were mild to moderate events that resolved in few days without treatment. No deaths, discontinuations, or SAEs were reported.

A safety monitoring plan has been developed to carefully monitor safety during the current study. An independent data monitoring committee (IDMC) will review unblinded safety, efficacy, pharmacodynamic (PD) and PK data every month based on a study specific IDMC Charter developed prior to study initiation. At any time, the IDMC may recommend stop patient treatment and/or terminate study based on pre-specified treatment discontinuation and study stopping rules.

Furthermore, investigators will be instructed to use local clinical laboratory for safety assessments in a timely manner.

Therefore, benefit/risk assessment did not indicate any significant concern at this stage.

More detailed information about the known and expected benefits, risks, and reasonably expected AEs of SIR1-365 can be found in the current IB of SIR1-365.

## 3. Trial Design

### 3.1. Overall Design

This will be a multicenter, randomized, double-blinded, placebo-controlled study to evaluate safety and efficacy of SIR1-365 in hospitalized patients with severe COVID-19. The primary objective is to assess the overall safety and tolerability of SIR1-365 administered orally at 100 mg, three times per day (TID) for up to 14 consecutive days relative to the placebo group. The secondary objectives are to assess the effects of SIR1-365 on clinical efficacy endpoints, and the biomarkers indicative of inflammation, target engagement and kidney injury as well as SIR1-365 PK.

Approximately 60 eligible patients will be randomly assigned at a 1:1 ratio to receive either SIR1-365 at 100 mg, TID or matching placebo for up to 14 consecutive days. Patients could be hospitalized for up to 14 days. Patients will be assessed daily while hospitalized. If the patients are discharged from the hospital before Day 14, all the assessments planned for Day 14 should be carried out before discharge. If a patient is still hospitalized after Day 14, no study drug will be administered after the last dose on Day 14.

It is preferred that the follow-up visit is in person to obtain safety laboratory tests. However, infection control or other restrictions may limit the ability of the patients to return to the clinic. In this case, the follow-up visit may be conducted by phone and only safety data will be obtained. Study drugs will not be administered for early discharged patients.

All randomized patients will receive standard supportive medical care for treatment of COVID-19 throughout the study. Follow-up visit will be scheduled approximately on Day 28 ( $\pm 3$ ) or 14 ( $\pm 3$ ) days after the last dose for those who are discharged from the hospital before Day 14.

SIR1-365 will be administered orally either as intact tablets with water if patient can swallow or as disintegrated suspension form to be delivered via a nasogastric (NG) tube if patient cannot swallow. Food and water will be allowed as needed.

[figure not shown]
To fit into the clinical practice of treating patients with severe COVID-19, screening visit and baseline visit can be combined in some patients. In that case, the number of dosing could be less than 3 times on that day. ECG, laboratory test and other test results obtained within 24 hours prior to consent can be used as baselines.

Safety will be assessed based on the findings of adverse events (AEs), vital signs, safety laboratory tests per local lab, 12-lead electrocardiography (ECG) per local ECG machine, and physical

Clinical efficacy will be assessed by measuring

PaO2/FiO2 ratio, time to improvement of oxygenation, number of days without oxygen use, a WHO ordinal scale to assess clinical improvement, length of hospital stay, percentage of patients free of respiratory failure, and all-cause mortality.

Correlation of biomarker levels to efficacy and safety outcomes will be assessed by analyzing the changes in efficacy and safety outcomes in patient populations with different Baseline levels of inflammatory biomarkers.

For the measurement of trough and peak plasma SIR1-365 and metabolite levels, one blood sample will be collected from each patient within 30 min before and 2 hours ( $\pm 5$  min) after the 1st dose on Day 1, respectively. On Days 7 and 14, one blood sample will be collected within 30 min before and 2 hours ( $\pm 5$  min) after the 2nd dose, respectively. The harvested plasma sample will be split into 4 approximately equal aliquots: 2 for drug level analysis and [REDACTED] to be conducted by a central lab. Collected samples may also be used for the analysis of additional biomarkers and SIR1-365 metabolites in the future.

The overall duration of the study will be up to 35 days, including up to 7 days for screening, up to 14 days for treatment, and a follow-up visit on approximately Day 28 ( $\pm 3$  days) or 14 ( $\pm 3$ ) days after the last dose for those who are discharged from the hospital before Day 14.

For those patients who complete the 14-day treatment period with SIR1-365, the investigator will decide appropriate treatments for the period from Day 15 to Day 28.

If an additional dosing cohort, or extended evaluation phase is added to the protocol to allow a more complete examination of the safety and efficacy of the compound, the protocol will be amended, and the new cohort(s) added prior to completion of the current study.

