### **7.2.1. Follow-up for Patients Who Discontinued from Treatment/Study**

If the patients are discharged from the hospital before Day 14, it is preferred that the follow-up visit is in person to obtain safety laboratory tests and blood samples for biomarker analysis as well as clinical outcome data. However, infection control or other restrictions may limit the ability of the patients to return to the clinic. In this case, the follow-up visit may be conducted by phone and only safety data will be obtained.

Patients who complete the 14-day treatment should be instructed to have the scheduled follow-up visit on Day 28. If a patient determines he/she no longer wishes to participate in follow-up visit, all the procedures associated with Day 28/Early Discontinuation/End of Study (EOS) visit should be completed at the time of discontinuation.

In both cases, follow-up for AEs should occur as per the discretion of the investigator. It is vital to obtain follow-up data on any patient withdrawn because of an AE or SAE. In every case, efforts must be made to undertake protocol-specified safety follow-up procedures.

Refer to the schedule of assessments (SoA) for data to be collected at the time of study discontinuation, follow-up, and for any further evaluations that need to be completed.

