#### **8.1.4. WHO Ordinal Scale**

The WHO ordinal scale is a 10-level ordered categorical scale developed by a special committee at WHO to measure illness severity over time. The scale will be used to assess patients' clinical status during the study. A 2-point reduction on the score of WHO ordinal scale is considered as clinical improvement.

This endpoint will be collected 4 times during the study: Baseline, Days 7, 14, and 28.

The scale can be found in [Appendix 2](#).

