#### **9.9. Follow-up Visit on Day 28/End of Study (EOS)**

- Vital signs
- 12-lead ECG
- Routine clinical laboratory tests including [REDACTED] one at local laboratory
- Coagulopathy and cardiac function panels done at local laboratory
- Urinalysis
- Oxygen use and saturation (pulse oximetry)
- WHO ordinal scale
- AE/SAE assessment and concomitant medications/current procedures

If the patients are discharged from the hospital before Day 14, all the assessments planned for Day 14 should be carried out before discharge. If a patient is still hospitalized after Day 14, no study drug will be administered after the last dose on Day 14.

It is preferred that the follow-up visit is in person to obtain safety laboratory tests. However, infection control or other restrictions may limit the ability of the patients to return to the clinic. In this case, the follow-up visit may be conducted by phone and only safety data will be obtained. Study drugs will not be administered for early discharged patients.

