13.1.4 WHO ordinal scale

The WHO ordinal scale is a 10-level ordered categorical scale developed by a special committee at WHO to measure illness severity over time. This endpoint will be collected 4 times during the study: at Baseline and on Days 7, 14, and 28.

The scale will be used to assess patients' clinical status during the study. A 2-point reduction on the score of WHO ordinal scale is considered as clinical improvement.

When completing the WHO Ordinal Scale at Day 14/ EOT, if the patient has received physician orders to be discharged from the hospital, the score should be a 3 or less (*no longer hospitalized*).

Change and percentage change from Baseline to Days 7, 14, and 28 in the scores of WHO ordinal scale as a continuous variable will be summarized by visit and treatment.

A separate summary table will be produced, similar to what is described above, summarizing the results at Day 7 (assessments taking place on study day 7), Day 14 (assessments taking place on study day 14) and Day 28 (assessments taking place on study day 28). For any patients with missing Day 7 results, the Day 7 results will be imputed using the last value reported prior to study day 7. Similarly, Day 14 missing observations will be imputed with the last available assessment that took place after study day 7 and prior to study day 14. Day 28 missing observations will be imputed with the last available assessment that took place after study day 14. A summary table will be produced, summarizing these (imputed and reported) results.

Categorical summaries of patients having a clinical improvement during the study (Baseline to Day 28) will be generated presenting the number and percentage of patients with an improvement at any visit from Baseline to Day 28. Associated 95% CI for the proportion of improvement will be provided for each treatment group using the Clopper-Pearson method.

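### Phone follow-up that records only safety data leaves discharged patients without a Day 28 WHO score, and oxygen-free days after discharge have no counting rule

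*Protocol*

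**What the plan says.** Follow-up in person is preferred. If infection control or another restriction keeps a discharged patient away, Protocol 3.1 allows a call, in which case "the follow-up visit may be conducted by phone and only safety data will be obtained". The same rule stands in the synopsis, sections 7.2.1, 8 and 9.9, Schedule of Assessments footnote 12, SAP section 5 and section 4 of the PK/PD analysis plan. Section 7.2.1 shows what the in-person visit is for: "safety laboratory tests and blood samples for biomarker analysis as well as clinical outcome data".

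The efficacy endpoints reach Day 28. They include "Change from Baseline to Days 7, 14 and 28 in the score of the WHO ordinal scale" and the number of days without oxygen to Day 28. On the WHO scale, Protocol 8.1.4 states: "This endpoint will be collected 4 times during the study: Baseline, Days 7, 14, and 28". Section 9.9 schedules the scale, oxygen use and pulse oximetry at the follow-up visit.

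For patients leaving before Day 14, "all the assessments planned for Day 14 should be carried out before discharge". SAP 8.4 tabulates those results as Day 14/EOT. SAP 13.1.4 then gives the Day 28 rule: "Day 28 missing observations will be imputed with the last available assessment that took place after study day 14". SAP 13.1.3 accumulates room-air time to the end of calendar Day 28.

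**The concern.** The rule on phone visits removes efficacy data from one kind of patient: someone who has left hospital. Those who remain are covered, since "Patients will be assessed daily while hospitalized", and a death scores 10 on the WHO scale. Missing Day 28 data are therefore linked to discharge, which is itself a favourable outcome. The carry-forward rule that might fill the gap is limited to a period in which an early-discharged, phoned patient normally has no assessment.

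At stake are the Day 28 WHO summaries and the oxygen-free-days estimate. The protocol justifies the sample size partly by the treatment-difference estimates it will supply for planning later studies. A Day 28 WHO mean drawn from a selected group, or an oxygen-free-days figure that rests on an unwritten choice, is weak planning material.

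**Working it through.** The plan states no discharge rate, phone rate or expected effect, so there is no figure to reproduce. The check sets the schedule against the imputation rules and then shows possible sizes under assumptions.

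**1. Carry-forward for the WHO score.** A patient discharged on, say, Day 9 has the last WHO score taken before discharge, so before Day 14. The next scheduled score is at follow-up. If that is a call, there is no score after study day 14 and nothing to carry. The EOT window of Day 14 (±2) can give a Day 15–16 value, but only for a patient still in hospital then. The other exception is an additional assessment after Day 14, for example during a readmission.

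**2. Oxygen-free days.** SAP 12.4 lists coagulopathy, cardiac function, PaO₂/FiO₂, WHO scale and CRP for carry-forward. Oxygen use is not listed. SAP 13.1.3 does not say how to treat time after the last oxygen record. The value is undefined rather than strictly missing. The visit date adds to this: follow-up for early discharge is 14 (±3) days after the last dose, so a last dose on Day 7 gives Days 18–24 and leaves time to Day 28 unobserved even after a clinic visit.

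**3. Other endpoints.**
- Two-point WHO improvement counts any visit (SAP 13.1.4), and a patient with a discharge order scores 3 or less. A patient starting at 5 is already a responder at discharge. One starting at 4 and leaving at 3 is not.
- Mortality is captured as safety data.
- Time to oxygenation improvement needs saturation above 93%, a rise of at least 1% and 48 hours on room air. It is measured daily in hospital and has a censoring rule (SAP 13.1.2). Only patients discharged before a qualifying reading are affected.

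**4. Number affected (both rates assumed).** Affected = 60 × share discharged by Day 14 × share of those phoned.
- Low: 60 × 0.7 × 0.3 = 12.6 (21%).
- High: 60 × 0.9 × 0.6 = 32.4 (54%).

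**5. Day 28 WHO mean (all inputs assumed).** Take 30 per arm, 85% (active) and 70% (placebo) discharged recovered with nothing to carry forward, a Day 28 score of 1.5 if recovered and 7 if not. With recovered share r and phone share q, the observed mean is [r(1−q)·1.5 + (1−r)·7] / [r(1−q) + (1−r)], and the number observed is 30(1 − rq).

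| Phone share q | Observed, active / placebo | Mean, active / placebo | Difference |
|---|---|---|---|
| 0% | 30 / 30 | 2.33 / 3.15 | −0.83 |
| 25% | 23.6 / 24.8 | 2.55 / 3.50 | −0.95 |
| 50% | 17.25 / 19.5 | 2.93 / 4.04 | −1.10 |
| 80% | 9.6 / 13.2 | 4.08 / 5.25 | −1.17 |

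With 80% discharged in both arms and equal phone shares, the difference stays at 0. Both means still rise, from 2.60 with no phone visits to 4.56 at 80% phone.

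**6. Oxygen-free days (all inputs assumed).** Use the same recovery shares and q = 50%. Recovered patients reach room air on Day 6 (active) or Day 9 (placebo) and leave two days later. The others have no room-air days.
- Room air carried to Day 28: 0.85 × 22 = 18.7 and 0.70 × 19 = 13.3, difference 5.4.
- Counting stops at discharge for phoned patients: 0.85 × (0.5 × 22 + 0.5 × 2) = 10.2 and 0.70 × (0.5 × 19 + 0.5 × 2) = 7.35, difference 2.85.
- Phoned patients excluded: 0.85 × 0.5 × 22 / 0.575 = 16.26 and 0.70 × 0.5 × 19 / 0.65 = 10.23, difference 6.03.

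The SAP chooses none of the three.

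**The case against.** The strongest reply is that phone contact is the exception, that clinic follow-up is preferred explicitly to get clinical outcome data, and that this is an exploratory phase 1b trial with a safety primary endpoint to Day 14. The WHO results are largely descriptive. All of this stands. It limits the consequence but does not fill the gap.

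A reader might infer that any efficacy endpoint running to Day 28 becomes selective. The documents do not support that: the any-visit rule and the discharge score protect most of the two-point improvement endpoint, and mortality is safety data.

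A reader might also infer that a call could recover everything. It cannot. Saturation needs a reading. WHO levels 0 and 1 are separated by viral RNA, and the in-person visit in section 9.9 lists no viral test either.

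Nor is readmission wholly lost, because hospitalization for an adverse event is a serious event and is collected to the end of participation. The possible gap is readmission for COVID-19 itself: Appendix 4 gives hospitalization for the disease under study as an example of what may fall outside the SAE definition.

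**Conclusion.** The point holds for two outcomes. A patient discharged before Day 14 and then phoned has no Day 28 WHO score and normally nothing eligible to carry forward. Oxygen-free days to Day 28 rest on an unstated choice for time after discharge. Time to oxygenation improvement is touched only at the margin.

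The size is unknown. The 13 to 32 patients, the WHO means and the oxygen-free-days differences all follow from assumed rates. That the missing patients are mostly recovered is an inference from who can be phoned; the documents do not report it. It would also go too far to conclude that the comparison between arms is biased. For the WHO mean, that needs discharge or phone rates to differ by arm, and with equal rates the illustration gives no difference. The selection of who contributes to the Day 28 WHO summaries remains in either case. The primary safety endpoint is not affected. The change is worth making because it is cheap and these estimates are meant for later planning.

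**What to change.** **Protocol and plan text.** In the protocol synopsis, 3.1, 7.2.1, 8, Schedule of Assessments footnote 12 and 9.9, SAP section 5, and PK/PD plan section 4, have the phone visit collect safety data plus:
- current oxygen use, and the dates of any oxygen use since discharge;
- any readmission since discharge, including for COVID-19;
- WHO ambulatory status as 0–1 combined (asymptomatic), 2 or 3.

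**SAP 12.4, 13.1.3 and 13.1.4.**
- Use the phone data for the Day 28 WHO score and for oxygen-free days. State which number the combined 0–1 category takes in the change from Baseline.
- If Day 28 WHO data are still missing, allow the discharge/EOT score to be carried forward as a labelled sensitivity analysis.
- Count post-discharge time as room air if the patient left on room air and no later oxygen use is reported. Add a sensitivity analysis that stops counting at discharge.

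**Cost.** One eCRF page and a few questions on a call already planned. Self-reported oxygen use is less precise than a clinic record, and saturation after discharge stays unavailable for phoned patients.
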